Has CITI or NIH Human Subjects Research Training been completed in the last 3 years:

Yes **No**

Responsibilities for this study (Choose letters from list above and/or write in any others):

A B C E F H I

Evaluation of Effects of Human-Animal Interaction on Physiological and Psychological Markers in Graduate Students
AHI - GHE Research Protocols

Question 9 continued:

Protocol parameters:

- https://vitaltrackusa.com/product/vitaltrack-blood-pressure-monitor/?_gl=1*fevef8*_gcl_aw*R0NMLjE3NDczMzU5ODMuQ2owS0NRandvWmJCQmhEQ0FSSXNBT3FNRVpXdTI3Mjg1NFFMcnhmcDJjNXRocE5xVHFQSzNIMWJKMENEbUpub3A4UUZiaTAtb3N2aURIVWFBldhRUFMd193Y0I.*_gcl_au*MTcxOTE0NTI1Ni4xNzQ3MzM1OTgz*_ga*MTq5ODcxMTkxNC4xNzQ3MzM1OTgz*_ga_RFZQ8VX21D*czE3NDczMzU5ODMkbzEkZzAkdDE3NDczMzU5ODMkaJYwJGwwJGgw

- 5-minute rest before each BP measurement
- Use the same BP cuff for consistency
 - If we have 2 BP cuffs, we'll mark them A and B for tracking purposes
- Automated BP (check with manual cuff if BP is high)
- Pulse Oximeter:
 - https://vitaltrackusa.com/product/vitaltrack-pulse-oximeter/?_gl=1*1aykaiq*_gcl_aw*R0NMLjE3NDczMzYxNDIuQ2owS0NRandvWmJCQmhEQ0FSSXNBT3FNRVpYR3Qza2R1VDFULTRzNENEUDIIWFdvNW8yZ0VPaGhRZkIKUWtMenp2Q3p1YTJpOEezRzZmZ2FBa1FFRUFMd193Y0I.*_gcl_au*MTcxOTE0NTI1Ni4xNzQ3MzM1OTgz*_ga*MTq5ODcxMTkxNC4xNzQ3MzM1OTgz*_ga_RFZQ8VX21D*czE3NDczMzU5ODMkbzEkZzEkdDE3NDczMzYxNDIkaJYwJGwwJGgw

- We need a 1st year schedule checker for subject availability.
 - Perhaps their V.P. could help?
- Qualtrics survey for inclusion/exclusion from the study.
- Randomization? www.Random.org

Outcome Measures:

The physiological outcomes of interest in this project are salivary cortisol levels, pain pressure thresholds, heart rate, and blood pressure. These objective measures will be tested (pre-intervention and post-intervention) at each of the four interaction sessions for both the control group (GHE) and experimental group (HAI). Once the data are collected, the researchers will evaluate each of the four parameters. Researchers would anticipate cortisol levels, blood pressure, and heart rate to decrease in response to decreased anxiety affiliated with HAI. On the other hand, pain pressure thresholds will likely increase in response to decreased anxiety.

The psychological outcomes of interest are the subjective reports on the Generalized Anxiety Disorder-7 (GAD-7) and Academic Anxiety Scale (AAS). The GAD-7 will be completed in the initial session and ending session only. The AAS will be completed at each of the four sessions to track the graduate students' academic anxiety week to week. For both subjective outcome measures, the lower the score the more indicative of decreased anxiety. Thus, researchers will be tracking scores weekly on the AAS and pre- to post-study for the GAD-7.

The short form C-BARQ is a 42-item survey completed by the owner/handler of a dog that specifically assesses Canine behaviors. The short form C-BARQ is a valid evaluation tool with higher scores indicating more severe behavioral problems.

Study Protocol:**Session 1:**

Read and sign consent form
GAD-7
AAS
HR & BP PRE-interaction
PPT PRE-interaction
Cortisol test
15-minute HAI (Room?)
15-minute GHE (Room?)
HR & BP POST-interaction
PPT POST-interaction

Session 2 & 3:

AAS
HR & BP PRE-interaction
PPT PRE-interaction
Cortisol test
15-minute HAI (Room?)
15-minute GHE (Room?)
HR & BP POST-interaction
PPT POST-interaction

Session 4:

GAD-7
AAS
HR & BP PRE-interaction
PPT PRE-interaction
Cortisol test

15-minute HAI (Room?)
15-minute GHE (Room?)
HR & BP POST-interaction
PPT POST-interaction

Question 10 continued:

Pressure algometer:

Beslands AMF-500 Digital Force Guage

https://www.amazon.com/live/video/0e288b878fc34c71b91fcfc9fa7d0e74?ref_=vse_cards_2

Please see attached manual.

Salivatory cortisol tests:

<https://salimetrics.com/assay-kit/salivary-cortisol-elisa-kit/>

Salivatory Cortisol Test Kits - <https://www.youtube.com/watch?v=azj5b0vA2Hk>

SALIMETRICS ASSAY #1-3002

Using a small sample volume, this assay kit has an extended range that spans the expected cortisol levels found in human saliva. The average inter- and intra-assay precision coefficients of variation are low with no deleterious matrix effects often found in saliva which are characterized through dilution- and spike-recovery validation procedures. The Salimetrics cortisol assay kit has also been formatted to minimize cross reactivity for related steroids. Salimetrics salivary assay kits are expertly designed, developed and validated to ensure accuracy in saliva and proven to deliver precision results for biomarkers in saliva. [Read More...](#)

Subject selection 6.2 continued...

...counseling or medications; students with known history of cardiac pathology and/or on cardiac medications.

List of included documentation:

- Co-investigator documentation
- Consent form
- Kansas Innovation Fund grant application
- Qualtrics email and Facebook announcement
- Non-acceptance email
- Generalized Anxiety Disorder (GAD-7)
- Academic Anxiety Scale (AAS)
- C-Barq questionnaire for therapy dog in training
- Algometer manual
- Algometer picture
- VitalTrack blood pressure cuff and pulse oximeter
- General Health Education (control group) documents:
 - 20 Benefits of Walking 30
 - How to deal with stress and anxiety
 - Sleep Hygiene
 - StressLess

GAD-7 Anxiety

Over the last two weeks , how often have you been bothered by the following problems?	Not at all	Several days	More than half the days	Nearly every day
1. Feeling nervous, anxious, or on edge	0	1	2	3
2. Not being able to stop or control worrying	0	1	2	3
3. Worrying too much about different things	0	1	2	3
4. Trouble relaxing	0	1	2	3
5. Being so restless that it is hard to sit still	0	1	2	3
6. Becoming easily annoyed or irritable	0	1	2	3
7. Feeling afraid, as if something awful might happen	0	1	2	3

Column totals _____ + _____ + _____ + _____ =

Total score _____

If you checked any problems, how difficult have they made it for you to do your work, take care of things at home, or get along with other people?

Not difficult at all

Somewhat difficult

Very difficult

Extremely difficult

Source: Primary Care Evaluation of Mental Disorders Patient Health Questionnaire (PRIME-MD-PHQ). The PHQ was developed by Drs. Robert L. Spitzer, Janet B.W. Williams, Kurt Kroenke, and colleagues. For research information, contact [name] at [contact]. PRIME-MD® is a trademark of Pfizer Inc. Copyright© 1999 Pfizer Inc. All rights reserved. Reproduced with permission

Scoring GAD-7 Anxiety Severity

This is calculated by assigning scores of 0, 1, 2, and 3 to the response categories, respectively, of "not at all," "several days," "more than half the days," and "nearly every day." GAD-7 total score for the seven items ranges from 0 to 21.

0–4: minimal anxiety

5–9: mild anxiety

10–14: moderate anxiety

15–21: severe anxiety

Academic Anxiety Scale

Please complete the following items using the four-point scale below.

1 = Not at all typical of me

2 = Somewhat typical of me

3 = Quite typical of me

4 = Very typical of me

1	I often worry that my best is not as good as expected in school.	1	2	3	4
2	I tend to put off doing schoolwork because it stresses me.	1	2	3	4
3	I often worry that I am not doing assignments properly.	1	2	3	4
4	I am less confident about school than my classmates.	1	2	3	4
5	I have a sense of dread when I am in my classrooms.	1	2	3	4
6	I tend to find my instructors intimidating.	1	2	3	4
7	I spend much of my time at school worrying about what is next.	1	2	3	4
8	There is something about school that scares me.	1	2	3	4
9	I'm concerned about what my classmates think about my abilities.	1	2	3	4
10	I often feel sick when I need to work on a major class assignment.	1	2	3	4
11	I have a hard time handling school responsibilities.	1	2	3	4

Scoring – simple addition of each item – no recoding required (range = 11-44). Finch et al (see below) have identified cut scores for different “levels” of Academic Anxiety based on the total score:

- Not Anxious – 11-14
- Mild Academic Anxiety – 15 – 20
- Moderate Academic Anxiety – 21 – 29
- High Academic Anxiety – 30 - 44

Citation Information for the Academic Anxiety Scale:

Cassady, J.C. (2020). *Academic Anxiety Scale*. Academic Anxiety Resource Center.
<https://sites.bsu.edu/aarc/research/academic-anxiety-scale/>

Related publications:

<https://www.frontiersin.org/articles/10.3389/feduc.2019.00011/full>

American Heart Association
Healthy for Good™

STRESS LESS WITH HEALTHY HABITS

1. Slow down.

Plan ahead and allow enough time to get the most important things done without having to rush.

2. Sleep well.

Try to get seven to nine hours of sleep each night. To fight insomnia, get regular physical and activity during the day.

3. Let worry go.

The world won't end if a few things fall off your plate. Give yourself a break and just breathe.

4. Laugh it up.

Laughter makes us feel good. Don't be afraid to laugh out loud, even when you're alone.

5. Get connected.

A daily dose of friendship is great medicine. Make time to call friends or family so you can catch up.

6. Get organized.

Use "to do" lists to help you focus on your most important tasks and take big projects one step at a time.

7. Practice giving back.

Volunteer your time or spend time helping a friend. Helping others helps you.

8. Be active every day.

Exercise can relieve mental and physical tension. Find something you enjoy and stick with it.

9. Give up the bad habits.

Too much alcohol, tobacco or caffeine can increase blood pressure. Cut back or quit to decrease anxiety.

10. Lean into things you can change.

Make time to learn a new skill, work toward a goal, or to love and help others.

Learn more at

[heart.org/HealthyForGood](https://www.heart.org/HealthyForGood).

© Copyright 2024 American Heart Association, Inc., a 501(c)(3) not-for-profit. All rights reserved.
Healthy for Good is a trademark of the AHA. Unauthorized use prohibited. WF497900 3/24

EAT SMART MOVE MORE BE WELL

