7.1c. Will the WSU PI oversee or coordinate the research being conducted at non-WSU sites? Yes No

If yes, Describe the PI's oversight plans, including how the PI will ensure adherence to the study protocol, obtain informed consent, secure and maintain IRB approval at the other sites, monitor adverse events or other unanticipated problems, and ensure general coordination of study conduct.

8. Please summarize the purpose of the proposed research using non-technical language that can be readily understood by someone outside the discipline:

The purpose of the study is to evaluate the effects of human-animal interaction on physiological and psychological markers in graduate students.

Graduate students face significant anxiety due to demanding coursework, long hours of studying, intense academic challenges, and the pressure to excel. Chronic stress in this population can contribute to elevated anxiety levels and measurable physiological changes, such as increased heart rate and blood pressure.

Human-animal interaction (HAI) and its effect on student stress, test anxiety, and physiological markers have been studied on college campuses, largely focusing on undergraduate students. However, research investigating the impact of HAI on graduate student stress, test anxiety, and physiological markers in high-stakes programs is limited. This study will evaluate the effectiveness of repeated HAI on graduate students' physiological markers and anxiety. The results of this study will assist participants, students outside this study, and the program administrators to appreciate the immense value of a full-time therapy dog on campus facilitating the human-animal bond in higher education.

9. Describe each procedure step-by-step, including the frequency, duration, and location of each procedure. A numbered or bulleted list of steps is helpful. *Submit a separate Word document if additional space is needed.*

Research Study:

*Location at [name], specific rooms TBD,

*Completed in the Fall 2025 semester,

*Frequency 1 time per week for 4 weeks,

*https://wichitastate.co1.qualtrics.com/jfe/preview/previewId/fe71f770-cbe3-414e-9174-865c7a4135db/SV_e9UIEaLk6Jdx0wu?Q_CHL=preview&Q_SurveyVersionID=current

Interventions:

Experimental: Human-animal interaction (HAI) - 15 minutes with therapy dog in training in groups of 2-3 participants, spending time doing what the participant wants to do (e.g., sitting quietly with the dog or playing with toys),

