Control: General Health Education (GHE) - 15 minutes in groups of 2-3 participants being educated on anxiety-relieving techniques and concepts; handouts provided for the participants reference,

Sessions:

1. At session 1, each participant will read and sign the consent form. Each will complete the Generalized Anxiety Disorder-7 (GAD-7) anxiety assessment and the Academic Anxiety Scale (AAS); have blood pressure and heart rate taken with automated blood pressure cuff and O2 monitor respectively (pre- and post-interaction); complete a baseline salivatory cortisol test, complete a baseline pain pressure threshold measurement.

2. At sessions 2 & 3, each participant complete the AAS; have blood pressure and heart rate taken with automated blood pressure cuff and O2 monitor respectively (pre- and post-interaction); complete a salivatory cortisol test, complete a pain pressure threshold measurement.

3. At session 4, each participant will complete the GAD-7 and AAS; have blood pressure and heart rate taken with automated blood pressure cuff and O2 monitor respectively (pre- and post-interaction); complete a final salivatory cortisol test, complete a final pain pressure threshold measurement.

(Continued on supplemental attachment...)

10. Instruments:
 
 Standardized Tests  Questionnaire  Interview  Internet  Other (specify): See supplement...
	
11. Recorded by:
 
 Written Notes  Audiotape  Videotape  Photograph/film  Standard mail  Webcam/digital camera
	
12. Administered:
 
 In person (group)  In person (individual)  Telephone  Mail  E-Mail  Other (specify):
	
13. Findings used for....
 
 Publication  Dissertation, Thesis  Needs assessment  Evaluation  Results to be released to:

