
14. Data will include: (Check all variables, if no personal identifiers will be accessed please mark this box )
			

 Names of People  Mailing or Email Addresses  Phone or Fax Numbers  Age  Gender  Ethnicity  Marital Status  IP Address  Date of Birth  License, Certificate or Vehicle ID  Social Security Numbers  Medical Record Number  Admission/Discharge Date  Account Numbers
	
 Finger or voice print  Photographic image  Web URL  Biometric Identifiers  Income  Student ID#  Job Title  Names of employers  Types of employers  Other Information:
	
Blood pressure, heart rate, pain pressure thresholds, salivatory cortisol markers.
	

15. Will this study involve the use of existing data, documents, records, and pathological specimen?  Yes  No If "Yes", include a letter of authorization to access data if not publicly available.
			

16. Do you anticipate using any data from this study for other studies in the future?  Yes  No
			

If "Yes", explain:
			

17. Is this study similar or build upon a previous study approved by WSU IRB?  Yes - IRB# 5778 (similar to)  No
			

18. Do you intend to publish or present the study's findings?  Yes  No
			

Subject Selection
			

1. Number of Subjects or Records to be accessed: Not more than 30 participants
			

2. Age of Subjects: 20-35
			

3. Will all participants be fluent in English?  Yes  No
			

4. Vulnerable populations to be recruited (check all that apply):
			

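### Does the GAD-7 at session 4, listed ahead of the fourth interaction, make the before-and-after comparison wrong?

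*Protocol*

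**What the plan says.** Item 9 of the protocol sets the programme at "Frequency 1 time per week for 4 weeks", each experimental contact being "15 minutes with therapy dog in training in groups of 2-3 participants". The control arm receives health education of the same length. Item 8 gives the aim: "This study will evaluate the effectiveness of repeated HAI on graduate" students' physiological markers and anxiety.

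On the GAD-7, the Outcome Measures text in the supplement to Question 9 says "The GAD-7 will be completed in the initial session and ending session only", and a little further on concludes "Thus, researchers will be tracking scores weekly on the AAS and pre- to post-study for the GAD-7". Item 9, step 3, agrees on the visit: "At session 4, each participant will complete the GAD-7 and AAS". It attaches no timing relative to the interaction to either questionnaire.

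The Session 4 list under Study Protocol opens with "GAD-7 AAS HR & BP PRE-interaction". It continues with the pressure-threshold reading, the cortisol test, the 15-minute interaction or education, and the repeat heart rate, blood pressure and pressure-threshold readings. The GAD-7 line has no tag placing it before or after the interaction. No visit after session 4 is described. The GAD-7 form itself asks about the preceding two weeks.

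**The concern.** A comparison described as running from before the study to after it suggests that the second form is completed once the whole programme has been delivered. Read as a time sequence, the Session 4 list says otherwise: the form comes first and the fourth interaction comes later that day.

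That reading is the natural one. The Session 1 list starts with consent, which has to come first. Every list puts the PRE readings before the interaction and the POST readings after it. The GAD-7 sits in the same place in sessions 1 and 4, so if that place makes the session 1 form a true baseline, it also makes the session 4 form pre-interaction.

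What would be at stake is interpretation. The GAD-7 is one of only two anxiety measures and the only one described as a before-and-after comparison. A report that credited its change to all four sessions would overstate the exposure, because a form completed before the fourth interaction cannot reflect it.

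**Working it through.** The protocol gives no effect size, standard deviation or power figure for the GAD-7, so there is no planned figure to reproduce. The check is a count of exposure and of recall days.

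**Inputs**
- Four weekly sessions of 15 minutes each (Item 9).
- GAD-7 at sessions 1 and 4 only (Outcome Measures).
- GAD-7 recall period of two weeks, i.e. 14 days (GAD-7 form).
- Five minutes' rest before each blood pressure reading (Protocol parameters).
- Assumption: sessions fall exactly on days 0, 7, 14 and 21.
- Assumption: the session list is in order of administration.

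**Exposure before each form**
- First GAD-7: 0 of 4 interactions.
- Last GAD-7: sessions 1, 2 and 3, so 3 of 4 interactions. Minutes: 3 × 15 = 45 of 4 × 15 = 60, or 75%.

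These are counts of scheduled contact. They do not convert into a percentage loss of effect.

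**What the last form asks about**

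The recall window runs from the day of completion minus 14 to the day of completion.

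| When the second GAD-7 is given | Window (days) | Days after session 4 |
|---|---|---|
| Session 4, before the interaction | 21 − 14 = 7 to 21 | 0 of 14 |
| Session 4, after the interaction | 7 to 21, shifted by minutes | 0 of 14 |
| One week later | 28 − 14 = 14 to 28 | 28 − 21 = 7 of 14 |
| Two weeks later | 35 − 14 = 21 to 35 | 35 − 21 = 14 of 14 |

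The first two rows are the ones that matter. The recall period is 14 × 24 × 60 = 20,160 minutes. Moving the form from the top of the session 4 list to the bottom shifts the window by the 15-minute interaction, two 5-minute rests (15 + 5 + 5 = 25 minutes) and the time for the readings, which is not stated. The 25 minutes are 25 / 20,160 = 0.12% of the recall period. The absence of any recall day after session 4 therefore comes from giving the form in session 4 at all. It does not come from where in session 4 the form sits.

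**What the listed position does capture**
- Baseline window: days −14 to 0, before any interaction.
- Session 4 window: days 7 to 21, taking in session 3 on day 14 and session 2 at its edge on day 7.
- The two windows do not overlap, and both forms are completed at the same point of a visit, before any contact with the dog that day. The change is therefore a like-for-like comparison.

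**The label against the schedule**

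The sentence with the label begins by drawing a conclusion from the schedule just stated, under which the GAD-7 is given at the initial and ending sessions. Read in context, the label is shorthand for first session to last session. It agrees with Item 9 and with both session lists, so no two statements conflict.

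**The case for a change.** The best case for a change is that it costs almost nothing. Tagging one line and rewording one phrase would need no new data, would keep timing uniform if different researchers run the sessions, and would stop a reader from crediting the GAD-7 change to four sessions. If a result for the complete programme is wanted, one further form for a study of "Not more than 30 participants" is a small burden.

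Part of this stands. On the natural reading, three interactions precede the last form, and a report should say so. The rest does not amount to a fault in the plan:

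- The order is inferred. The lists are rough in other respects: they stack the two alternative arms one after the other, and they show a single untagged cortisol test although Outcome Measures has cortisol taken before and after. They are weak evidence for the timing of an untagged line.
- The protocol does not promise a GAD-7 result for the complete programme. It speaks of repeated interaction, and the harm arises only if someone later claims more than that.
- Placing the form at the end of session 4 would make the label literally true while leaving almost the same fortnight under recall.
- A form one or two weeks later adds a contact beyond the four sessions, invites non-response in a small sample, and measures persistence after the programme. That is a defensible alternative question, but nothing in the protocol calls for it.

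**Conclusion.** The observation about the listed order is right, but no change to the plan follows. On that order the GAD-7 comparison runs from baseline to the start of session 4, after 3 of 4 interactions (45 of 60 minutes). The label is imprecise, but it fits the schedule the protocol states alongside it. Timing is the same in both arms, so the contrast between animal interaction and health education is not biased and the plan as written gives no wrong result. Given the two-week recall, the position within session 4 hardly alters what is measured. A later form would be a trade-off and not a correction.

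This rests on two assumptions: that the list is chronological and that sessions are exactly weekly. If the form is in fact given after the interaction, the label is literally correct and the question disappears. In either case, an analyst can describe the result accurately by stating when in session 4 the form was completed.

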6.1 What are the primary inclusion criteria?

Enrolled and active first-year graduate students at Wichita State University,
Participants between the ages of 20 and 35.

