6.2 What are the primary exclusion criteria?

Students with diagnosed dog allergies; students with a fear of dogs; students diagnosed with mental health disorders; students with ongoing mental health treatment including (con't...)

7. Is Compensation Offered? Yes No If "Yes", describe amount, type (gift card, greenphire, etc) and when:

8. Describe the recruitment process, including any advertisements (flyers, emails, phone scripts, Strategic Communications Ads, etc.) to be used for this study. Include the flyer and text of the ads, emails, scripts as applicable in a separate document.

Participants will be recruited via an in-person presentation and explanation of the study by the research team.

Participants will be given the opportunity to sign up and navigate inclusion/exclusion criteria via a Qualtrics survey via a link sent through email from the PI.

https://wichitastate.co1.qualtrics.com/jfe/preview/previewId/fe71f770-cbe3-414e-9174-865c7a4135db/SV_e9UIEaLk6Jdx0wu?Q_CHL=preview&Q_SurveyVersionID=current

Risks/Benefit Information

1. Potential Risk Exposure: Physical (cognitive or motor) Psychological Economical Legal Social

2. Describe the nature and degree of the risks. (Do not say N/A - It cannot be assumed that there are no risks). Be sure all items listed are described in the informed consent document.

1. Minor physical risk from the human-animal interaction,
2. Minor physical risk from the salivatory cortisol test,
3. Minor physical risk for pain due to the pain pressure threshold testing/algometer.

3. Describe how risks and discomforts (physical, psychological, or social) will be minimized:

1. Risks due to animal interaction are minimized by having the animals trainer present, the animal having canine good citizen certification, and currently working through progression towards therapy dog certification.

2 & 3. Physical risks will be limited by training researchers and educating participants on research parameters.

2. All researchers will be properly trained how to obtain a salivatory cortisol test.
3. All researchers will be properly trained on the use of the pain pressure threshold algometer.

4. Please describe the benefits of the research to human subjects, if any, and of the benefits to human or scientific knowledge:

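### Salivary cortisol is a named outcome, but the shown protocol neither screens for corticosteroid use or endocrine disorder nor fixes or records the time and conditions of sampling

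*Protocol*

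**What the plan says.** Under Outcome Measures the protocol states: "The physiological outcomes of interest in this project are salivary cortisol levels, pain pressure thresholds, heart rate, and blood pressure". The four are listed together, with no ranking.

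Inclusion (item 6.1) requires "Enrolled and active first-year graduate students at Wichita State University" and age 20 to 35. Exclusions (item 6.2 and its continuation in the supplement) are dog allergy, fear of dogs, a diagnosed mental health disorder, "students with ongoing mental health treatment including" counselling or drugs, and "students with known history of cardiac pathology and/or on cardiac medications". The list ends there. Screening is by a "Qualtrics survey for inclusion/exclusion from the study", whose items are not shown.

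The protocol parameters in the supplement (Question 9 continued) set a 5-minute rest before each blood pressure reading and consistent use of the cuff. They set no condition for cortisol or pain pressure threshold (PPT). Sessions run once a week for four weeks with no time of day given. On scheduling there is only a planning note: "We need a 1st year schedule checker for subject availability".

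On the number of cortisol samples the protocol disagrees with itself. Outcome Measures says the objective measures are taken before and after the intervention at each of the four sessions. The session lists under Study Protocol show one cortisol test per session, placed before the interaction, with none after. Item 9 of the application also describes one cortisol test per session.

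**The concern.** Corticosteroid use and adrenal or endocrine disorder act directly on the measured quantity, and salivary cortisol also falls through the day. A student in either group meets every criterion shown. A student sampled in the morning one week and the afternoon the next has followed the protocol exactly.

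What is at stake is whether a cortisol difference can be read as a response to the intervention. This is protocol content and not a matter for a later analysis plan: a sample time or a medication that was never recorded cannot be adjusted for or examined afterwards. The protocol parameters go down to labelling two cuffs A and B, so this is the level of detail at which such rules belong.

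**Working it through.** The protocol gives no figure on this point to reproduce. The check is of the text, followed by arithmetic for scale under stated assumptions.

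**1. Which contrast does cortisol support?**
- If the session lists hold, there is one pre-interaction sample per session. The only change available is from one week to another, so any difference in clock time between weeks goes straight into it.
- If Outcome Measures holds, there is also a within-session change. A shift of the whole session then largely drops out, and the decline over the session is common to both arms.

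**2. Size of a clock-time shift.** Assumption: cortisol declines during the day at a rate k of 0.08 to 0.12 per hour. The change from moving a session by h hours is 1 − exp(−k·h). The values of k and h are not in the protocol.

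| Interval | k = 0.08 | k = 0.12 |
|---|---|---|
| 15 minutes (one interaction) | 1 − exp(−0.02) = 2% | 1 − exp(−0.03) = 3% |
| 2 hours | 1 − exp(−0.16) = 15% | 1 − exp(−0.24) = 21% |
| 4 hours | 1 − exp(−0.32) = 27% | 1 − exp(−0.48) = 38% |

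The across-week contrast is therefore the exposed one.

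**3. Chance imbalance.** The protocol caps enrolment at 30. Assume 15 per arm and m corticosteroid users among the 30. The probability that all fall in the same arm is 2·C(30−m, 15)/C(30, 15).
- m = 2: 2 × (15·14)/(30·29) = 48%
- m = 3: 2 × (15·14·13)/(30·29·28) = 22%
- m = 4: 2 × (15·14·13·12)/(30·29·28·27) = 10%

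**4. Loss of precision.** With 15 per arm, two-sided alpha 0.05 and a normal approximation, the standardised difference detectable with 80% power is (1.960 + 0.842) × √(2/15) = 1.02. If uncontrolled sampling conditions add a share v to the outcome variance, power for that difference is Φ(2.802/√(1+v) − 1.960), and the number per arm that restores 80% is 15 × (1+v). The values of v are assumptions.
- v = 10%: power 76%; 16.5, so 17 per arm
- v = 25%: power 71%; 18.75, so 19 per arm
- v = 50%: power 63%; 22.5, so 23 per arm

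Each of these exceeds the 15 per arm that a cap of 30 allows.

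**The case against.** Several stronger readings are tempting, and the protocol does not support them.

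*Clock times will shift and steroid users will be enrolled.* The scheduling note is an open planning item, and one session a week is compatible with a fixed weekly slot. The text leaves times unfixed; it does not say that they move. It allows corticosteroid users in, but does not show that any will come.

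*The exclusions were written to protect heart rate and blood pressure only.* No reason is given for the cardiac exclusion, which may be there for safety. The mental health treatment exclusion also removes some drugs that could act on cortisol or pain.

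*The comparison is biased.* A control arm runs concurrently on the same weekly schedule. If allocation is random, uncontrolled timing and intake bring mainly noise and chance imbalance. Bias would need the arms to run at different hours, or intake to drift apart by arm. Neither is stated. It remains possible: randomization is still written as a question, sessions are held in groups of two or three, and the control handouts advise limiting caffeine and exercising daily.

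*All four outcomes are equally damaged.* PPT, heart rate and blood pressure are listed before and after each 15-minute session, so stable drug use and time of day partly cancel. Likewise, one of 15 participants with cortisol near zero at every visit lowers the arm's level by about 1/15 = 7%, but contributes almost no change, which dilutes an effect and does not create one.

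*No instructions exist.* Item 6.2 asks "What are the primary exclusion criteria", so the list may be partial. The screening items are not shown, and the acceptance email is said to carry instructions that are not shown. The absence is established only for the text at hand.

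What stands after this: the shown protocol has no clock-time rule, no record of sample time and no corticosteroid or endocrine screen for a named cortisol outcome.

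**Conclusion.** The point holds in a limited form, and mainly for cortisol. As written, the protocol can admit corticosteroid users and people with adrenal or endocrine disorder, and it neither holds nor records the time and conditions of sampling. The conflict over one or two cortisol samples per session must be reconciled. If one sample holds, a 2-hour difference between weeks may change a participant's cortisol by about 15-21% without any treatment effect, assuming a fall of 8-12% per hour. The expected consequence is lost precision and chance imbalance in at most 30 people, not a demonstrated bias. The imbalance and power figures rest on assumed user counts, variance shares and an even split, none of which the protocol gives.

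**What to change.** - Reconcile Outcome Measures with the session lists on how many cortisol samples are taken per session and when.
- Add current corticosteroid use and known adrenal or endocrine disorder to item 6.2 and to the Qualtrics screen.
- In the protocol parameters, hold each participant's four sessions at the same clock time (for example within 1 hour), spread both arms over the same hours, and record the time of each sample.
- Ask participants to avoid food, caffeine, nicotine and exercise for a fixed period before sampling, with a reminder in the acceptance email.
- Record recent intake and any medication, including analgesics, on a short checklist at each session, without restricting medication. Use the record in a sensitivity analysis of cortisol and PPT.

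Broader exclusions for chronic pain, analgesics or other drugs are not needed for this purpose and would narrow a small recruitment pool.

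The cost is a few screening items, one line in an email, and one recorded time and one checklist per session. The downside is slightly fewer eligible students and less freedom in scheduling.
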